5. TRIAL TREATMENT

5.1 Manufacturing and Labelling of Investigational Medical Product

5.1.1 Identity

CyPep-1 is a synthetic linear 27-amino acid peptide with an acetylated amino group at the N-terminus and an amido group at the C-terminus. All optically active amino acid residues are in D-configuration with the exception of achiral glycine. CyPep-1 is formulated in a clear and colorless aqueous solution (5 mg/mL).

5.1.2 Packaging and Labelling

The intratumoral formulation of CyPep-1 is a liquid dosage form for subcutaneous administration supplied in single-use vials. The CyPep-1 5 mg/mL solution consists of the drug substance CyPep-1 dissolved in 0.9% NaCl solution. Each vial contains a deliverable volume of 2 mL of CyPep-1 solution corresponding to 10 mg of the drug substance CyPep-1, present as acetate salt. An additional overfill is included in each vial to ensure that the labelled amount of 10 mg of CyPep-1 (corresponding to 14 mg of the acetate salt) can be delivered.

5.2 Instructions for Use, Handling, and Storage

The preliminary proposed shelf life of the CyPep-1 injectable solution is 18 months upon the date of manufacture, when stored at $5 \pm 3^\circ\text{C}$ (protected from light). The product may be kept outside the proposed storage condition at temperatures up to 25°C for up to 3 days to cover short-term temperature excursions (e.g. during shipping, labelling, and handling).

Pembrolizumab should be used, handled and stored in line with institutional guidelines.

5.3 Treatment Regimen

The overall study treatment regimen is defined as intratumoral CyPep-1 as monotherapy (Phase I and Phase IIa Arms A, C and D) and in combination with pembrolizumab (Phase IIa Arm B).

The interventions to be used in this trial are outlined below in [Table 2](#).

Table 2. Trial Interventions

Intervention Name	Dosage Formulation	Unit Dose Strength(s)	Dosage Level(s)	Route of Administration	Regimen/Treatment Period	Sourcing
Pembrolizumab (MK-3475)	Solution for infusion	100 mg/vial	400 mg Q6W	IV infusion	Until end of trial or confirmed PD, unacceptable toxicity, death or discontinuation for any other reason for a maximum of 18 treatment cycles.	As provided by sponsor
CyPep-1	Solution for injection	See Section 5.3.1		Intratumoral	See Section 5.3.1	Provided centrally by the Sponsor

5.3.1 Administration of IMP (CyPep-1)

Administration will be through a needle inserted trans-dermally. The needle should be redirected along multiple tracks to ensure even dispersion of CyPep-1 throughout the lesion. For Arm C, CyPep-1 will be administered via intralesional injection with ultrasound guidance into one metastatic liver lesion.

A detailed guidance for intratumoral administration of CyPep-1 is presented in the Study Procedural Manual.

5.3.1.1 CyPep-1 Dose Levels

For Phase I, in three dose cohorts of 3 subjects each, subjects received CyPep-1 intratumorally at different concentrations (dose escalation) and volumes (depending on tumor size), i.e., 0.5 mg/mL, 2 mg/mL, or 5 mg/mL, respectively.

The CyPep-1 concentration for each dose cohort of the dose escalation (Phase I) was as follows:

Dose cohort	CyPep-1 concentration
1	0.5 mg/mL
2	2 mg/mL
3	5 mg/mL

Subjects in Phase IIa expansion arms (Arms A, B and D) of the trial will be treated at the CyPep-1 RP2D dose determined in Phase I. Based on the review of all safety data for the three dose cohorts and recommendation by the DEC (dated 09 Sep 2021), a RP2D for CyPep-1 is 5.0 mg/mL to be taken forward in Phase IIa.

During the dose expansion in liver metastases (Arm C), the safety and tolerability of at least two dose levels of CyPep-1, the RP2D (cohort 5) and the dose immediately below that (cohort 4), are planned to be evaluated when CyPep-1 is administered intratumorally into 1 single lesion in the liver.

5.3.1.2 CyPep-1 Injection Volume

The total amount of CyPep-1 injected will depend on the tumor volume(s). The volume delivered to each lesion selected for injection will be determined based on the longest diameter measured by the most accurate measurement technique available for each lesion (e.g. caliper, CT, or MRI) at screening and every 8 weeks during the iRECIST/itRECIST assessments. A chosen technique used at screening will be consistently used throughout the study. Lesion sizes need to be checked before each injection by either caliper (mandatory for Arm D and to-be-injected cutaneous/subcutaneous lesions for Phase IIa Arms A and B) or other imaging modalities used to guide CyPep-1 injections, i.e., ultrasound, CT or MRI, . For Arm C, , the lesion size measurement will be performed by the same imaging modality used to guide CyPep-1 injections. To ensure consistency of the measurements, the sites need to strive for having the same operator to perform all measurement for a chosen measuring technique. If there are major changes in the lesion size, the injection volume may be adjusted based on the ultrasound measurements per investigator's opinion and consultation with the Medical Monitor is possible.

For both phases of the trial, the cumulative maximal injected volume will be 4 mL per treatment day, corresponding to a cumulative maximal dose of 20 mg of CyPep-1 (with the maximal concentration of 5 mg/mL of CyPep-1, which is the RP2D). Effort should be made to administer the maximum planned injection volume of CyPep-1 as planned per lesion size (see tables below).

For Phase I, Phase IIa Arms A and B, the to-be-injected volume may be divided for injection over 1-3 tumor lesions (e.g., one large lesion or 2-3 relatively small lesions). In case more than 3 lesions are good candidates for injection, the to be injected lesions selection can be discussed with the sponsor and the medical monitor.

For Phase IIa Arm C, CyPep-1 will be administered with ultrasound guidance into one metastatic liver lesion. The same single metastatic lesion is to be injected with CyPep-1 based on lesion size.

For Phase IIa Arms A and B, for a lesion > 7 cm, the same lesion should be considered to be injected weekly with up to 4 mL of CyPep-1 for the first 6 weeks (on Day 1, 8, 15, 22, 29 and 36), independent of the potential change in lesion size, followed by Q2W 4 mL administrations of CyPep-1. The visits on Days 1, 15, 29 and 36 will follow the assessments as per schedule. The visits on Days 8 and 22 will follow the assessments as per D15 (C1V2; excluding central lab sampling for cytokine analysis and blood sampling for immune cell phenotyping).

For Phase IIa Arm D, the to-be-injected volume for injection is preferably divided over as many lesions as possible. The longest diameter of the lesions for injection is ideally smaller than 2 cm and should not exceed 5 cm.

For subjects in Arms A, B and C, the injection volume will be:

Measured Lesion Diameter (cm)	Injected volume (mL)
≤ 1	1
> 1 and ≤ 2	2
> 2	4

For subjects in Arm D, the injection volume will be:

Measured Lesion Diameter (cm)	Injected volume (mL)
≤ 0.79	0.1
0.80 to 0.99	0.2
1.00 to 1.24	0.5
1.25 to 1.50	1.5
1.51 to 2.49	3.0
≥ 2.50	4.0

5.3.1.3 Sequence of CyPep-1 Administration for Phase IIa Arm D Only

Lesion Map

A lesion map that will guide the preferred sequence of injection of the identified Lesion Sets must be created prior to the first CyPep-1 injection (detailed in Study Procedural Manual). A lesion map will contain the following information:

For superficial lesions:

- Digital color photography of the lesions must be taken and the mark-ups of individual lesions (or lesion groups) with lesion ID are overlayed on top of the digital photography.
- Silhouette of body parts must be used to present the relative location of the lesions.
- All digital color photography containing a ruler held next to the longest diameter of the lesion to indicate the size of the lesion, and the lesions marked-up with lesion IDs, together with the silhouette of body parts indicating the location of the lesions, need to be submitted to eCRF with inspection readiness for the reported responses.
- In the case of bilateral lesions, the laterality of the lesions must be documented on the lesion map.

For deep lesions:

- CT or MRI scan will be used for iRECIST/itRECIST assessment at baseline, and the location of lesions provided by the CT/MRI scan will be used.

- In the case of bilateral lesions, the laterality of the lesions must be documented on the lesion map.

Once the lesion map is created, Lesion Sets for sequential CyPep-1 injections will be planned and documented in the source. The size of the injected lesions and the lesion map should be updated when assessments of local measurements of tumor lesions, iRECIST and itRECIST assessments are performed during the treatment period.

Lesion Sets

A Lesion Set will be composed of multiple lesions, and will be administered with CyPep-1 during the same treatment visit for three consecutive doses. Unless there are no other Lesion Sets to be injected, each Lesion Set will not receive more than three consecutive doses of CyPep-1. In the case of bilateral lesions, both of the bilateral lesions should be included in the same lesion set if feasible considering the maximum injected volume allowed per treatment visit (4 mL).

The sequence of CyPep-1 Administration

After three doses of CyPep-1, the next Lesion Set will be administered with CyPep-1. The ideal next to-be-injected lesion set should be located as far as possible from the last injected Lesion Set on the lesion map to activate different draining lymph nodes and thus optimize a systemic immune response against the tumor. Once all injectable lesions have been injected and the subject remains on treatment, a new lesion map that permits reprioritizing of the to-be-injected lesion sets will be created, taking into account size changes of individual lesions, e.g., an individual lesion enlarged or regressed after initial 3 doses of CyPep-1 injections.

5.3.2 Administration of Pembrolizumab

The dose of pembrolizumab in combination with CyPep-1 in the combination arm (Arm B) will be 400 mg Q6W. Pembrolizumab will be administered using IV infusion on Day 1 of each 6-week treatment cycle after all procedures and assessments have been completed.

Dosing of CyPep-1 will be aligned such that subjects will receive both pembrolizumab and the first dose of CyPep-1 on the same day (C1V1). After C1V1, pembrolizumab dosing will continue following a Q6W dosing scheme until 18 cycles, confirmed PD, unacceptable toxicity, death, or consent withdrawal. Trial treatment of pembrolizumab may be administered up to 3 days before or after the scheduled Day 1 of each cycle due to administrative reasons after the first administration (C1D1).

On the visits that CyPep-1 and pembrolizumab are administered on the same day, CyPep-1 is planned to be administered 30 to 60 min after pembrolizumab is administered. In case of pembrolizumab-related toxicity, treatment with CyPep-1 will be delayed and planned after a review by the investigator and medical monitor.

Pembrolizumab will be administered as a dose of 400 mg using a 30-minute IV infusion. Sites should make every effort to target infusion timing to be as close to 30 minutes as possible. However, given the variability of infusion pumps from site to site, a window between -5 minutes and +10 minutes is permitted (i.e., infusion time is 30 minutes [-5 min/+10 min]).

The Pharmacy Manual contains specific instructions for the preparation of the pembrolizumab infusion and administration of infusion solution.

5.3.3 Meals and Dietary Restrictions

Participants should maintain a normal diet unless modifications are required to manage an AE such as diarrhoea, nausea, or vomiting.

5.3.4 Selection of CyPep-1 Doses in the Trial

In Phase I of the trial, CyPep-1 will be administered intratumorally in escalating doses as follows:

1. Cohort 1: 0.5 mg/mL on Day 1 of Weeks 1, 3, and 5 (Days 1, 15, and 29)
2. Cohort 2: 2 mg/mL on Day 1 of Weeks 1, 3, and 5 (Days 1, 15, and 29)
3. Cohort 3: 5 mg/mL on Day 1 of Weeks 1, 3, and 5 (Days 1, 15, and 29)

Continuous Q2W administration of CyPep-1 is planned after Day 29.

Selection of these doses was based on previous preclinical experience with CyPep-1 ([Szczepanski et al, 2014](#)). The total amount of CyPep-1 injected will depend on the tumor volume. The volume delivered to each lesion selected for injection will be determined based on the longest diameter measured by the most accurate measurement technique available for each lesion (e.g. caliper, CT, or MRI) at screening and every 8 weeks during the iRECIST/itRECIST assessments (see [Section 5.3.1.2](#)). Before each injection, the longest diameter of the lesion will be measured. The approximate injected volume per lesion will be 1 - 4 mL for lesions <1.5 cm, 2 - 4 mL for lesions ≤ 4 cm, 3 - 4 mL for lesions > 4 cm. Efforts should be made to administer the maximum volume of CyPep-1 per administration as per dose level.

For Phase IIa Arms A, B and C, weekly administration schedule for the first 6 weeks should be considered for a lesion > 7 cm followed by Q2W administration.

The proposed CyPep-1 starting dose for the clinical trial is obtained from the therapeutic range identified in the nonclinical in vitro (0.025 mg/mL) and *in vivo* intratumoral studies (1-5 mg/mL (refer to [IB](#)). The data suggests that the starting dose of 0.5 mg/mL in the tumor microenvironment is within the identified range to achieve an initial and meaningful biological effect. Since intravascular administration can occur during intratumoral injection, the NOEL from IV administration studies was considered relevant to identify the first dose. Based on the 7 days toxicology study of repeat IV bolus with CyPep-1, the NOEL of 3,0 mg/kg was identified in rats. The corresponding HED is 0,48 mg/kg (0.16 x 3,0 mg/kg). For a 70 kg person this equals 33.6 mg. As the maximal cumulative starting dose in trial is 2 mg, a safety factor of 16.8 has been taken into account, considering that the route of administration is intratumoral instead of IV with limited systemic exposure anticipated.

Planned doses in the trial:

- 2 mg/mL (cumulative 8 mg) and 5 mg/mL (cumulative 20 mg)
- CICILIA Phase I dose escalation used IT administered CyPep-1 (comparable to subcutaneous administration study showing ~100-fold lower Cmax / ~20-fold lower AUC compared to IV with an ~ 5% bioavailability).
- AE summary of RP2D determined during Phase I: 5 mg/mL dose (20 mg CyPep-1) resulted in related TEAEs of injection site pain Grade 1 and 2 (AE number = 12) without DLTs, SAEs or AEs leading to discontinuation.

In Phase IIa of the trial, all subjects will receive intratumoral CyPep-1 at the doses specified in [Section 5.3.1](#).

Phase I, the dose escalation part of the CICILIA trial, has been completed. The determined RP2D of IT administered CyPep-1 was 5 mg/mL. The MTD was not reached. The CyPep-1 dose to be applied in Phase IIa Arms A, B and D is 5 mg/mL.

For cohorts 4 and 5 of Phase IIa Arm C, the doses of CyPep-1 to be investigated are 2 mg/mL and 5 mg/mL, respectively.

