For Phase I and Phase IIa, Arms A, B and C, CyPep-1 will be administered intratumorally Q2W, on Day 1, 15, and 29 of each cycle. In the absence of DLT/TLTs during Cycle 1, treatment continues with Q2W IT injections of CyPep-1. For Arm D, CyPep-1 will be administered intratumorally QW until the second iRECIST/itRECIST assessment at week 16, followed by a Q2W dosing scheme. For all phases/arms, treatment will continue until confirmed PD, unacceptable toxicity, death, or consent withdrawal, loss to follow up, or trial end, whichever occurs first (for discontinuation refer to Section 4.3.1).

Administration will be through a needle inserted trans-dermally. The needle should be redirected along multiple tracks to ensure even dispersion of CyPep-1 throughout the lesion. For Arm C, CyPep-1 will be administered via intralesional injection with ultrasound guidance into one metastatic liver lesion. A detailed guidance for intratumoral administration of CyPep-1 is presented in the Study Procedural Manual.

The CyPep-1 concentration for each dose cohort during dose escalation (Phase I) is as follows:

Dose cohort	CyPep-1 concentration
1	0.5 mg/mL
2	2 mg/mL
3	5 mg/mL

The total amount of CyPep-1 injected will depend on the tumor volume(s). Effort should be made to administer the maximum planned injection volume of CyPep-1 as planned per lesion size.

CyPep-1 Injection Volume:

The volume delivered to each lesion selected for injection will be determined based on the longest diameter measured by the most accurate measurement technique available for each lesion (e.g. caliper, CT, or MRI) at screening and every 8 weeks during the iRECIST/itRECIST assessments. A chosen technique used at screening will be consistently used throughout the study. Lesion sizes need to be checked before each injection by either caliper (mandatory for Arm D and to-be-injected cutaneous/subcutaneous lesions for Phase IIa Arms A and B) or other imaging modalities used to guide CyPep-1 injections, i.e. ultrasound, CT, or MRI. For Arm C, the lesion size measurement will be performed by the same imaging modality used to guide CyPep-1 injections. To ensure consistency of the measurements, the sites need to strive for having the same operator to perform all measurement for a chosen measuring technique. If there are major changes in the lesion size, the injection volume may be adjusted based on the ultrasound measurements per investigator's opinion and consultation with the Medical Monitor is possible.

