
For both phases of the trial, the cumulative maximal injected volume will be 4 mL per treatment day, corresponding to a cumulative maximal dose of 20 mg of CyPep-1 (depending on the dose concentration). Effort should be made to administer the maximum planned injection volume of CyPep-1 as planned per lesion size (see tables below).

For Phase I and Phase IIa Arms A and B, the to-be-injected volume may be divided for injection over 1-3 tumor lesions (e.g., one large lesion or 2-3 relatively small lesions). In case more than 3 lesions are good candidates for injection, the to be injected lesions selection can be discussed with the sponsor and the medical monitor.

For Arm C, CyPep-1 will be administered with ultrasound guidance into one metastatic liver lesion. The same single metastatic lesion is to be injected with CyPep-1 based on lesion size.

For Arms A and B, for a lesion > 7 cm, the same lesion should be considered to be injected weekly with up to 4 mL of CyPep-1 for the first 6 weeks (on Day 1, 8, 15, 22, 29 and 36), independent of the potential change in lesion size, followed by Q2W 4 mL administrations of CyPep-1.

For Arm D, the to-be-injected volume for injection is preferably divided over as many lesions as possible. The longest diameter of the lesions for injection is ideally smaller than 2 cm and should not exceed 5 cm.

For subjects in Arms A, B and C, the injection volume will be:

Measured Lesion Diameter (cm)	Injected volume (mL)
≤ 1	1
> 1 and ≤ 2	2
> 2	4

For subjects in Arm D, the injection volume will be:

Measured Lesion Diameter (cm)	Injected volume (mL)
≤ 0.79	0.1
0.80 to 0.99	0.2
1.00 to 1.24	0.5
1.25 to 1.50	1.5
1.51 to 2.49	3.0
≥ 2.50	4.0

For all subjects, if a lesion disappears at any time, the investigator may choose another lesion for subsequent injections. Previously non-injected lesions may also be injected if necessary (e.g. safety reasons), per investigator's discretion.

Sequence of CyPep-1 Administration for Phase IIa Arm D only:

Lesion Map

A lesion map that will guide the preferred sequence of injection of the identified Lesion Sets must be created prior to the first CyPep-1 injection (detailed in Study Procedural Manual). A lesion map will contain the following information:

For superficial lesions:

- Digital color photography of the lesions must be taken and the mark-ups of individual lesions (or lesion groups) with lesion ID are overlayed on top of the digital photography.

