The change in T-cell receptor (TCR) clonality levels will be assessed in the available peripheral blood samples. To assess the hypothesis that CyPep-1 increases the TCR clonality systematically, which suggests that T-cells are targeting the tumor, the clonality diversity metric will be computed for all subjects providing peripheral blood samples at screening and/or Week 6 of every CyPep-1 treatment cycle. Based on preliminary on file data of TCR clonality analysis in peripheral blood dated Nov 2022, the dataset collected is sufficient for the intended analysis and further sampling will provide no additional insights. Uncertainty about the representativeness of data generated with blood samples regarding TCR changes in the tumor microenvironment has lead Cytovation to reconsider this scientific relevance of this assay. Therefore, Cytovation decided to stop collecting blood samples for TCR clonality analysis for all subjects. TCR sequencing might be performed on the available remaining tumor biopsy material from the analyses of changes in the tumor microenvironment. Overlaps of T cell clones in respect to expansion and breadth of T cell clonality before and after intratumoral injection with CyPep-1, as monotherapy and in combination with pembrolizumab (central analysis) will be analyzed.

The change in tumor microenvironment is examined via the expression of selected candidate immune markers by immunohistochemistry. For each marker, a difference in expression will be explored.

Changes in cytokine levels and in frequency of various immune cell types in peripheral blood (immunophenotyping) will be explored.

SCHEDULE OF ASSESSMENTS

The schedule of all assessments performed within the context of this clinical trial is provided in Tables 1a to 1d.

Table 1. Schedule of Assessments

Table 1a. Schedule of Assessments Phase I Dose Escalation and Phase IIa Arms A and C for Cycle 1 (CyPep-1 Monotherapy)

	Screening ¹	DLT observation period			Continued Treatment	EoT ²	FU ³	PFS-FU ⁴	OS-FU ⁵
Week	1	3	5	6					
Day	-28 to 1	D1	D15	D29	D36				Every 3 months
Visit no.	Screening	C1V1	C1V2	C1V3	C1V4				
Visit window	NA	-	± 3 d	± 3 d	± 3 d	± 3 d	-	-	-
Informed consent	X					See Table 1b			
Demography	X					Subsequent cycles ⁶			
Medical and surgical history ⁷	X								
Eligibility	X	X							
Tumor biopsy ⁸	X				X ²⁸				
Performance (ECOG) status ⁹	X	X	X	X	X	X	X	X	X
Height ⁹	X								
Weight ⁹	X	X	X	X	X	X	X	X	X
Physical examination ⁹	X	X	X	X	X	X	X	X	X

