Vital signs ¹⁰	X	PRE- & 15m, 30m, 1h, 2h, 4h POST-dose	PRE- & 15m, 30m, 1h, 2h, 4h POST-dose	PRE- & 15m, 30m, 1h, 2h, 4h POST-dose	X	X	X	X	X
Electrocardiogram ¹¹	X	X	X	X	X				
Hematology and biochemistry ¹²	X	X	X	X	X	X	X	X	X

	Screening ¹	DLT observation period					Continued Treatment	EoT ²	FU ³	PFS-FU ⁴	OS-FU ⁵
Week	1	3	5	6							
Day	-28 to 1	D1	D15	D29	D36						
Visit no.	Screening	C1V1	C1V2	C1V3	C1V4						
Visit window	NA	-	± 3 d	± 3 d	± 3 d						
Creatinine clearance ¹³	X										
Coagulation ¹²	X	X	X	X							
Urinalysis ¹²	X	X	X	X							
Pregnancy test ¹⁴	X	X	X	X							
PK (first 9 subjects Phase I + all subjects Arm C) ¹⁵											
Cytokines ¹⁶	X		X								
Blood sampling for immune cell phenotyping ¹⁷	X		X								
Local measurement of tumor lesion(s) ¹⁸		X	X								
Administration of CyPep-1 ¹⁹		X	X	X							
Concomitant medication ²⁰	X	X	X	X							
AEs ²¹	X	X	X	X							
iRECIST assessment ²²											
Evaluation of survival and subsequent anti- cancer therapies											X

At 8-week (±3 days) intervals while on trial treatment²³

Table 1b. Schedule of Assessments Phase I Dose Escalation and Phase IIa Arms A and C (Starting Cycle 2 and all subsequent cycles monotherapy)²⁴

Week	1	3	5	6
Day	D1	D15	D29	D36
Visit no.	Cycle X Visit 1 ²⁵ (CXV1)	CXV2	CXV3	CXV4
Visit window	± 3 d	± 3 d	± 3 d	± 3 d
Weight	X			
Physical examination	X	X	X	
Vital signs ¹⁰	PRE- & 15m, 30m, 1h, 2h, 4h POST-dose	X	X	
Tumor biopsy	X ²⁶			X ²⁶
Performance (ECOG) status ⁹	X			
Hematology and biochemistry ¹²	X			
Urinalysis ¹²	X			
Pregnancy test ¹⁴	X	X	X	
Cytokines ¹⁶			X ²⁷	
Blood sampling for immune cell phenotyping ¹⁷			X	
Local measurement of tumor lesion(s) ¹⁸	X	X	X	
Administration of CyPep-1 ¹⁹	X	X	X	
Concomitant medication ²⁰	X	X	X	X
AEs ²¹	X	X	X	X
iRECIST assessment ²²				At 8-week (+3 day/s) intervals while on trial treatment ²³

Table 1c. Schedule of Assessments Phase IIa Arm B (Cycle 1 CyPep-1 plus pembrolizumab combination)

	Screening ¹	TLT observation period			Continued Treatment	EoT ²	FU ³	PFS-FU ⁴	OS-FU ⁵
Week	1	3	5	6					
Day	-28 to 1	D1	D15	D29	D36				
Visit no.	Screening	C1V1	C1V2	C1V3	C1V4				
Visit window	NA	-	± 3 d	± 3 d	± 3 d	± 3 d	± 1 wk	± 1 wk	± 1 wk
Informed consent	X								
Demography	X								
Medical and surgical history ⁷	X								
Eligibility	X								
Tumor biopsy ⁸	X					X ²⁸			
Performance (ECOG) status ⁹	X		X	X	X	X	X		
Height ⁹	X								
Weight ⁹	X	X	X	X	X	X	X	X	
Physical examination ⁹	X	X	X	X	X	X	X	X	X

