during or after IT administration, it is recommended to provide celecoxib 400 mg as premedication every 6 hours for 24-48 hours. Premedication should be administered for subsequent CyPep-1 doses based upon clinical judgment and presence/severity of prior reactions. This regimen may be modified based on local treatment standards and guidelines as appropriate. To ensure prophylactic hydration, subjects should consume ≥ 2 L of fluid intake per day, starting ≥ 48 hours prior to first dose/each dose escalation and for ≥ 24 hours thereafter. For subjects who have difficulty to maintain adequate oral hydration, intravenous hydration is recommended, at an infusion rate of 150-200 mL/hr (i.e., $2\text{-}3$ L per day) for initial dosing; for following dose escalations, an intravenous hydration with 1.5-2 L per day is advisable. For lesions > 7 cm, weekly CyPep-1 administration should be considered by the Investigator for the first 6 weeks, on Days 1, 8, 15, 22, 29 and 36 of cycle 1. The assessments are as per scheduled visit for Day 1, 15 and 29. Visits on Day 8 and 22 will follow the assessments as per D15 (C1V2) with the exclusion of central lab sampling for cytokine analysis and blood sampling for immune cell phenotyping. For Day 36 assessments as specified in the schedule need to be performed, with additional assessments: Pre-dose ECG, Vital Signs PRE- & 15m, 30m, 1h, 2h, 4h POST-dose, Coagulation and Pregnancy test (if applicable).

20. All concomitant medication/procedures should be reported beginning upon ICF signature until FU (or EoT, if it occurs more than 30 days after the last CyPep-1 or pembrolizumab administration).

21. Reporting period is from ICF signature until FU (or EoT, if it occurs more than 30 days after the last CyPep-1 or pembrolizumab administration). After the FU visit (or EoT, if it occurs more than 30 days after the last CyPep-1 or pembrolizumab administration), only ongoing (S)AEs related to CyPep-1 or pembrolizumab administration will be collected. Adverse events will be assessed using CTCAE v5.0 including start and stop dates, severity, relationship to CyPep-1 or pembrolizumab, outcome and action taken.

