The safety and tolerability of at least two dose levels of CyPep-1, namely the RP2D and the dose immediately below that, are planned to be evaluated when CyPep-1 is administered intratumorally using ultrasound guidance to one metastatic lesion in the liver. The two dose levels are planned to be investigated adhering to the 3+3 design and will follow the procedures as described for the dose escalation (Phase I) (Section 3.1). The first three subjects will receive CyPep-1 at the lower dose level and each subject will be observed for 24 h before CyPep-1 administration to a next subject (cohort 4). After the third subject at that dose finished the DLT observation period of 6 weeks (5 weeks CyPep-1 treatment plus 1 week safety follow-up), the DEC will decide on the start of the cohort to be administered at RP2D based on the review of the safety data (cohort 5). In the absence of any DLTs in the first 3 subjects, the 24-h observation period before start treatment of the next subject is not applicable. After the DLT observation period for the first three subjects at RP2D for CyPep-1 and the review of all safety data, the DEC will recommend on the inclusion of all remaining subjects. Should a DLT be observed in the first three subjects at the RP2D of CyPep-1, an additional three subjects in this dose group will be included. In case that two or more subjects experience DLTs at RP2D of CyPep-1, a recommendation to dose de-escalate and to what dose and how to continue Arm C will be made by the DEC.

Phase IIa – dose expansion melanoma subjects (Arm D):

The safety and tolerability of CyPep-1 at RP2D will be further evaluated with focus on assessing efficacy signals of CyPep-1 monotherapy in up to 30 subjects with melanoma. Although safety information will be collected, there will not be a formal DLT observation period. The dosing scheme starts with a once weekly (QW) CyPep-1 administration until the second iRECIST/itRECIST assessment at week 16, followed by a Q2W dosing scheme.

As part of the continuous safety monitoring of the trial, reports with cumulative safety data of Arm D subjects will be shared with all investigators, competent authorities, and ethical committees of countries where the trial is conducted at the following time points:

- After the first three subjects completed three weeks of treatment with CyPep-1.
- After the first three, six, and 12 subjects completed six weeks of treatment with CyPep-1.

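### The protocol contradicts itself on whether Arm C may be dosed weekly for a lesion over 7 cm, so one 3+3 dose level could mix 3- and 6-injection schedules

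*Protocol*

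**What the plan says.** Four places in the protocol state the weekly option for a lesion over 7 cm, and they do not agree on who may have it.

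- **Section 5.3.4**: "For Phase IIa Arms A, B and C, weekly administration schedule for the first 6 weeks should be considered", for a lesion above 7 cm. Arm C is included.
- **Section 5.3.1.2**: "For Phase IIa Arms A and B, for a lesion > 7 cm, the same lesion should be considered to be injected weekly". Arm C is not included.
- **Synopsis, CyPep-1 Injection Volume**: "For Arms A and B, for a lesion > 7 cm, the same lesion should be considered to be injected weekly". Arm C is not included.
- **Schedule of Assessments, footnote 19**: "For lesions > 7 cm, weekly CyPep-1 administration should be considered by the Investigator for the first 6 weeks". No arm is named. The footnote is attached to the CyPep-1 administration row of Table 1a, titled "Schedule of Assessments Phase I Dose Escalation and Phase IIa Arms A and C for Cycle 1 (CyPep-1 Monotherapy", whose PK row reads "PK (first 9 subjects Phase I + all subjects Arm C".

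The default schedule is clear. The synopsis says "For Phase I and Phase IIa, Arms A, B and C, CyPep-1 will be administered intratumorally Q2W, on Day 1, 15, and 29", and Table 5 likewise puts Arms A, B and C at Weeks 1, 3 and 5. Section 3.1 describes Arm C as a 3+3 evaluation that "will follow the procedures as described for the dose escalation (Phase I"). Its six-week DLT window consists of five treatment weeks and one week of safety follow-up. Section 5.3.1.2 requires every Arm C injection to go into the same liver lesion.

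**The concern.** A 3+3 decision rests on three to six subjects treated alike at one dose level. If a site follows Section 5.3.4 or footnote 19 for an Arm C subject with a large lesion, that subject is treated and observed differently from the others in the cohort. A second site following Section 5.3.1.2 would treat the same kind of subject every two weeks. One such subject is 1 of 3 in an initial group.

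Other Arm C rules assume three injections in the window. Replacement under Section 4.3.2 depends on whether all three were given. The delay rule in Section 4.3.1 identifies the DLT period with the first three injections, which on a weekly schedule would be Days 1, 8 and 15. No text says how a weekly-dosed subject counts in the 3+3 decision.

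Weekly dosing would also narrow the separation between the two dose levels. The arm is built cautiously, starting one level below the RP2D with 24-hour staggering in the first cohort, and an unplanned doubling of injections works against that.

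**Working it through.** **Inputs**

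- Every-two-week schedule: Days 1, 15 and 29 (synopsis; Table 1a).
- Weekly schedule: Days 1, 8, 15, 22, 29 and 36 (Section 5.3.1.2; footnote 19).
- Maximum volume: 4 mL per treatment day, and 4 mL for any lesion above 2 cm (Section 5.3.1.2).
- Arm C concentrations: 2 mg/mL in cohort 4 and 5 mg/mL in cohort 5 (Section 5.3.4).
- Window: treatment weeks 1 to 5 are Days 1 to 35 and follow-up week 6 is Days 36 to 42. Cycle 2 Day 1 is Day 43 (SAP Appendix 4).

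**The plan's own figure.** Section 5.3.4 gives cumulative daily doses of 8 mg at 2 mg/mL and 20 mg at 5 mg/mL. These reproduce: 2 × 4 = 8 and 5 × 4 = 20.

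**Maximum exposure in the DLT window**, as injections × 4 mL × concentration:

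| | Every two weeks | Weekly |
|---|---|---|
| Injections | 3 | 6 |
| Volume into one lesion | 3 × 4 = 12 mL | 6 × 4 = 24 mL |
| Dose at 2 mg/mL | 12 × 2 = 24 mg | 24 × 2 = 48 mg |
| Dose at 5 mg/mL | 12 × 5 = 60 mg | 24 × 5 = 120 mg |
| Injections on Days 36 to 42 | 0 | 1 |

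A weekly subject at the lower level could therefore receive 48 mg, against 60 mg for an every-two-week subject at the higher level.

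**Can such a subject be enrolled?** Section 4.1 sets a minimum size of 1 cm for Arm C and no maximum diameter, whereas Arm D has a 5 cm limit. The other relevant barrier is Section 4.2, exclusion 21 (more than one third of the liver involved). A 7 cm sphere has volume π/6 × 7³ = 179.6 mL. Alone it would breach that limit only in a liver smaller than 3 × 179.6 = 539 mL. The documents give no liver volume. At an assumed 1,200 to 1,800 mL the lesion is 179.6/1,200 = 15% down to 179.6/1,800 = 10%. The necrosis, location and vessel-invasion criteria make large lesions less likely but do not exclude them by size.

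**Illustration of the effect on the 3+3.** The documents give no DLT rate, so this rests on assumptions. Let the per-subject DLT risk be p on three injections and q = 1 − (1 − p)² on six. The chance that a level passes is P(0 of 3) + P(1 of 3) × P(0 of the next 3).

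| p | q | All every two weeks | One weekly subject in the first three | All weekly |
|---|---|---|---|---|
| 0.10 | 0.19 | 0.906 | 0.875 | 0.730 |
| 0.20 | 0.36 | 0.709 | 0.632 | 0.378 |
| 0.30 | 0.51 | 0.494 | 0.396 | 0.161 |

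**Does the SAP settle it?** No. Section 9.6.1 counts subjects on a weekly Cycle 1 schedule by cohort. Section 8.10 displays Arm C only as cohorts 4 and 5, and Section 10.2.5 plans no weekly-versus-every-two-week comparison. Appendix 4 lists Cycle 1 Days 8 and 22 in a column shared by Arms A, B and C, which neither shows nor excludes weekly dosing in Arm C.

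**The case against.** The strongest reply is that the protocol largely answers the question. Table 2 sends the CyPep-1 regimen to Section 5.3.1, and Section 5.3.4 itself refers Phase IIa doses there. In Section 5.3.1.2 the Arm C paragraph is followed directly by a weekly paragraph that names only Arms A and B. On this reading Section 5.3.4 contains a stray reference to Arm C. Footnote 19 is then generic text serving several tables: Table 1a also covers Phase I, for which no dosing section offers weekly treatment.

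Four further points reduce the weight.

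- Arm B has the same six-week window and a 3-then-6 toxicity rule, and weekly dosing is expressly open there.
- Exposure within a dose level already varies. Lesions of more than 1 and up to 2 cm receive 2 mL and larger ones 4 mL, so three injections already span 6 to 12 mL.
- The DEC reviews Arm C data before cohort 5 starts and again before the remaining subjects enter. The concentration and daily cap do not change, and footnote 19 adds safety checks at Day 36.
- The Study Procedural Manual and the Cohort Management Plan were not available and may clarify practice.

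Most of this stands as to weight. The documents as a whole favour Arms A and B, and harm requires a large eligible lesion, a site following the wrong text, an investigator using a discretionary option, and no correction by the medical monitor or the DEC. It does not remove the conflict. Section 5.3.4 names Arm C outright, and footnote 19 is the dosing instruction a site reads from its schedule. The Arm B comparison shows only that weekly dosing can be allowed when the text says so consistently. The existing volume range follows lesion size under one stated rule; weekly dosing would widen it from 6–12 mL to 6–24 mL without one.

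**Conclusion.** The inconsistency is real and lies in current protocol text. Sections 5.3.1.2 and 5.3.4 cannot both be followed for an Arm C subject with a lesion over 7 cm. The size is conditional: up to twice the injections, volume and dose in the DLT window, plus one injection in the week meant for follow-up. These maxima assume 4 mL at every visit and use of the weekly option throughout. How many of the 9 planned subjects would be affected is unknown, and the pass probabilities are illustrative only. The point deserves correction because it concerns dosing in a small liver-safety cohort whose other rules presume three injections. It does not call the overall design into question.

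**What to change.** In Section 5.3.4, limit the weekly sentence to Arms A and B. In footnote 19, begin the weekly sentence with a restriction to Arms A and B only. State explicitly that Arm C stays on Days 1, 15 and 29 through the DLT window. This brings both places into line with Section 5.3.1.2, the synopsis and Table 5. The cost is a wording amendment in two places, with no change to sample size, visits or assessments.

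If the sponsor does want weekly dosing in Arm C, all four places should say so, and the protocol should define how such a subject counts in the 3+3 decision and for replacement. The documents do not state the enrolment status of Arm C. If dosing is already complete, report each Arm C subject's actual schedule beside the DLT result.
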